1. INTRODUCTION

Perioperative pulmonary hypertension (PH) and right ventricular dysfunction (RVD) during cardiac surgery are serious complications associated with delayed weaning from cardiopulmonary bypass (CPB) and significant postoperative morbidity and mortality (1). Their pathophysiology is multifactorial and includes factors such as left ventricular systolic or diastolic dysfunction, the systemic inflammatory response associated with CPB, reduced pulmonary endothelial NO production during CPB, and pulmonary factors like pulmonary ischemia-reperfusion injury, surfactant dysfunction, increased susceptibility to pulmonary collapse, impaired pulmonary mechanics, and gas exchange impairment (2, 3). Inhaled nitric oxide (iNO) is a selective pulmonary vasodilator that has been successfully used to treat postoperative PH and RVD. Specifically, by reducing pulmonary arterial tone and resistance, iNO improves right ventricular (RV) performance despite its mild negative inotropic effect. Furthermore, iNO has been shown to effectively reduce pulmonary vascular resistance (4, 5), mitigate CPB-related inflammation (6), and more recently, reduce acute kidney injury and provide protection against chronic kidney diseases (7). Although clear benefits in outcomes have not been established, due to the aforementioned reasons, experts consider the use of iNO useful for perioperative treatment of increased pulmonary vascular resistance during cardiac surgery (8).

Recently, we have studied the effects of lung collapse on RV function during CPB weaning and have described that a ventilation strategy aimed at minimizing collapse and maintaining homogeneously ventilated lungs, known as open lung approach (OLA), improves RV performance (9). Lung collapse is present in the majority of patients after cardiac surgery, often affecting more than 10% of the total lung tissue mass (10). Lungs remain collapsed during CPB, receiving only minimal blood flow through bronchial arteries, without protection against ischemia. Furthermore, the inflammatory response triggered by CPB circulation inactivates surfactant. This, along with atelectasis induced during anesthesia induction, results in a lung highly prone to collapse in the immediate perioperative period. Lung collapse has several negative consequences for both pulmonary function and pulmonary circulation. On one hand, it reduces functional lung size, affecting pulmonary mechanics, increasing transpulmonary pressure, and impacting gas exchange, reducing ventilation efficiency and increasing the demand for inspired oxygen. On the other hand, lung collapse reduces the cross-sectional area of the pulmonary vasculature, and unventilated or under-ventilated alveoli trigger and enhance hypoxic pulmonary vasoconstriction response, which is further amplified in the presence of concurrent respiratory or metabolic acidosis. All these factors lead to increased pulmonary vascular resistance, early PH, and RVD. Right ventricular dysfunction is related to difficulties in weaning from CPB, an increased demand for catecholamines and inotropic support extending into the postoperative period, where it can complicate early recovery by prolonging dependence on drugs and mechanical ventilation, ultimately affecting the individual patient's outcome.

The increase in pulmonary vascular resistance and PH after cardiac surgery and their response to different therapeutic strategies like iNO have been well documented. However, there is limited information on how such measures affect RV function and their true influence on perioperative evolution. In this study, we aim to evaluate modifiable pathophysiological treatments for postoperative PH and RVD.

One pharmacological, iNO, and one non-pharmacological, the OLA strategy that combines lung recruitment and stabilization with individually optimized positive end-expiratory pressure (PEEP), and the possible synergistic effects of both interventions on RV performance. Apart from specifically targeting the described pathophysiological mechanisms, the combination of an OLA strategy and iNO could be especially beneficial, as modifying the pulmonary state through OLA could theoretically enhance the effects of iNO by significantly increasing the gas exchange area and, thus, alveolar ventilation. We will also study a series of closely related physiological variables to better characterize the effects of both strategies and their combination. This can help establish a better indication for iNO in cardiac surgery patients and improve our understanding of mechanisms that are also present in patients with acute respiratory distress syndrome (ARDS), albeit on a different scale.

2. Hypothesis

Inhaled nitric oxide (iNO) administered at a dose of 20 to 40 ppm in the immediate postoperative period of cardiac surgery improves pulmonary vascular mechanics and right ventricular function and synergistically interacts with alveolar recruitment in patients presenting with postoperative atelectasis.

3. Aims

Primary aim

- To study the effects of inhaled iNO on pulmonary vascular mechanics, right ventricular function, and right ventricular-vascular coupling in patients in the immediate postoperative period of cardiac surgery.

Secondary aim

- To compare the effects of iNO with standard care and with a lung recruitment maneuver on pulmonary vascular mechanics, right ventricular function, and right ventricular-vascular coupling in patients in the immediate postoperative period of cardiac surgery.
- To study patterns of redistribution of pulmonary blood flow measured by Electrical Impedance Tomography (EIT) that predict a positive effect on vascular mechanics and right ventricular function

4. Patients

Inclusion Criteria

Patients undergoing cardiac surgery who meet the following criteria will be included in the study:

- Age > 18 years
- Under controlled mechanical ventilation in passive conditions
- Presence of postoperative lung collapse (confirmed by pulmonary echocardiography and Air test)
- Preoperative left ventricular ejection fraction (LVEF) $\geq 30\%$.
- Absence of hypovolemia: absence of "kissing" ventricles and/or collapsibility index of the superior vena cava < 20%.
- Stable spontaneous heart rhythm
- Postoperative hemodynamic stability:
- Mean arterial pressure (MAP) ≥ 60 mmHg
- Central venous pressure (CVP) ≥ 10 mmHg

Versión 2: September 1, 2023

- Heart rate (HR) \leq 100 bpm without tachyarrhythmias
- Lactic acid \leq 3 mmol/L
- Single vasopressor treatment
- Norepinephrine dose \leq 0.2 $\mu\text{g}/\text{kg}/\text{min}$, without an increase \geq 15% in the last 30 minutes.
- Obtained informed consent

Exclusion Criteria

- Cor pulmonale or preoperative pulmonary vascular pathology
- Absence of pre-existing chronic respiratory pathology.
- Pre-induction arterial oxygen saturation (SpO₂) $<$ 97% by pulse oximetry
- Chronic pulmonary hypertension (mPAP $>$ 35 mmHg) related to advanced COPD r chronic thromboembolic disease.
- Tricuspid or pulmonary valve surgery.
- Intra or postoperative use of nitroprusside or nitroglycerin.
- Preoperative dependency on inotropic or vasoconstrictor drugs.
- Use of levosimendan. Patients receiving dobutamine may be included as long as the infusion is \leq 2 $\mu\text{g}/\text{kg}/\text{min}$.
- Contraindication for transesophageal echocardiography (See Appendix I) (11)
- Absence of lung collapse
- Pacemaker dependency

5. Methods

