5.3 Specific Study Interventions

5.3.1 Inhaled Nitric Oxide (iNO)

The iNO administration device will be the So Kinox™ (Air Liquide). This device is one of the best and safest clinical devices for administering inhaled nitric oxide, routinely used in the intensive care unit. It ensures accurate dosing of iNO regardless of inspiratory flow and volume. It continuously and accurately monitors the concentration of nitric oxide in inspired gas and the fractions of inspired oxygen and nitrogen dioxide, a toxic byproduct of nitric oxide. The product technical information is available in the supplementary documentation. iNO will be initiated at a dose of 20 ppm immediately after randomization in the corresponding groups. After 30 minutes, a first assessment will be performed, and the iNO dose can be increased to 40 ppm as long as there is no increase in methemoglobin levels above 2.5% and in case there is no improvement in ventricular function or ventricular-vascular coupling, defined by the presence of any of the following:

- $TAPSE \leq 16$ mm
- $TAPSE/PAPs \leq 0.26$
- $S' \leq 9$ cm·sec⁻¹
- $RVOT-AT \leq 100$ ms

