5.7 Study Groups

After confirming atelectasis using the air test and lung ultrasound, patients will be randomly assigned using block randomization to one of the following three groups:

1) Standard treatment (CONT): Patients will be managed according to routine clinical protocol, standardizing interventions in both participating centers.

2) iNO 20-40 ppm (iNO): iNO at 20 ppm will be initiated immediately after randomization and data collection. The dose will be re-evaluated after the first 30 minutes and may be increased to a maximum of 40 ppm depending on the observed response in ventricular function.

3) iNO 20-40 ppm + Pulmonary Recruitment (iNO-RM)

[figure not shown]

Figure 1: Study protocol

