5.7.1 Admission Evaluation

Upon admission, patient monitoring and stability will be checked. After routine arterial and venous blood gas extraction, the air test and lung ultrasound will be performed to determine the presence of atelectasis. If the presence of collapse is confirmed, informed consent will be obtained from the family if it has not been given previously. If affirmative, randomization will be conducted, and impedance belts will be placed.

5.7.2 Protocol Measurement Time Points:

T1: Admission

Baseline measurements will be taken upon arrival in the intensive care unit, once the patient has been monitored, postoperative atelectasis has been confirmed (using lung ultrasound or air test), and the patient is in a stable condition after initial laboratory tests.

T2: Baseline

30 minutes after the first measurement under reference ventilation conditions. Depending on the observed response in right ventricular function, the iNO dose will be adjusted. If no improvement is observed, the iNO dose will be increased to 40 ppm.

T3: Final

30 minutes after applying the specific protocol for each group.

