5.8.2 Statistical Methods

Variables will undergo descriptive analysis of central tendency measures including mean, median, dispersion, standard deviation, and interquartile range, respectively. Homoscedasticity and normality assumptions will be confirmed using Levene's and Shapiro-Wilk tests, respectively.

Variables with normal distribution and similar variance will be compared using the t-test, and variables with non-normal distribution using the non-parametric Wilcoxon test. Pearson's chi-squared test will be used for categorical variables to compare groups at the three measurement points in the study, and Fisher's exact test when expected frequencies are < 5 .

For the comparison of more than two means with homoscedastic variances and normal distribution, ANOVA with post hoc testing will be conducted. For variables with heteroscedastic variances and/or non-normal distribution, the Kruskal-Wallis post hoc test will be applied. To analyze temporal evolution, a repeated measures ANOVA will be used with the intervention type as the main factor. In case of non-normality, the non-parametric Friedman test will be applied. Statistical significance will be set at $p \leq 0.05$. Statistical analysis will be performed using Stata v.15.

6. Safety and Adverse Events

To ensure safety during the 2-hour duration of the research protocol, the following precautions will be taken:

The inclusion of unstable patients or those who have had significant intraoperative complications leading to instability will be avoided.

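### The hypothesis claims synergy between iNO and lung recruitment, but no patient is studied with recruitment alone, so the three arms cannot confirm it

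*Protocol*

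**What the plan says.** Section 2 (Hypothesis) has two parts: that iNO improves pulmonary vascular mechanics and right ventricular function, and that it "synergistically interacts with alveolar recruitment in patients presenting with postoperative atelectasis". The Introduction also lists "the possible synergistic effects of both interventions on RV performance" among the matters to be evaluated.

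The first secondary aim in section 3 is "To compare the effects of iNO with standard care and with a lung recruitment maneuver on pulmonary vascular mechanics", continuing to right ventricular function and coupling.

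Section 5.7 randomises to three groups: CONT, iNO, and "3) iNO 20-40 ppm + Pulmonary Recruitment (iNO-RM"). The last is the only group that receives recruitment.

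On timing, section 5.3.1 says "iNO will be initiated at a dose of 20 ppm immediately after randomization in the corresponding groups". Section 5.7.2 places T2 "30 minutes after the first measurement under reference ventilation conditions", and the iNO dose is reassessed at that point. T3 follows 30 minutes after each group's specific protocol.

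Section 5.8.2 says that for change over time "a repeated measures ANOVA will be used with the intervention type as the main factor".

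**The concern.** Synergy means that the combined effect exceeds the sum of the separate effects. To show it, one must know what recruitment does without iNO, and this trial never observes that.

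The risk is a false positive claim. The Introduction reports that the ventilation strategy "known as open lung approach (OLA), improves RV performance (9), and section 5.8.1 plans on a 15% improvement from either iNO or recruitment. On those premises iNO-RM should do better than iNO even if the two treatments simply add. That expected result would look like support for the second clause of the hypothesis, although an additive recruitment effect explains it equally well.

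The secondary aim is also ambiguous. If it means iNO against recruitment alone, that comparison has no matching arm. If it means iNO given together with recruitment, it can be estimated.

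**Working it through.** **Inputs.** The arms are from section 5.7 and the timing from sections 5.3.1 and 5.7.2. Section 5.8.1 gives 18 patients per arm and a 15% improvement. Section 5.8.2 sets significance at 0.05, taken here as two-sided. The protocol gives neither an SD nor a power, so its total of 54 cannot be reproduced from stated inputs. It is attainable: by the normal approximation, 18 per arm gives 80% power for a 15-point difference if the SD is 15 / (2.802 × √(2/18)) = 16.1. The structural result below uses none of these figures.

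**Step 1: what the arms identify.** Let b0 be the mean under standard care, b1 the iNO effect, b2 the effect of recruitment without iNO, and b3 the interaction. Synergy is b3 > 0.

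| Arm | Expected mean | Design row (b0, b1, b2, b3) |
|---|---|---|
| CONT | b0 | 1, 0, 0, 0 |
| iNO | b0 + b1 | 1, 1, 0, 0 |
| iNO-RM | b0 + b1 + b2 + b3 | 1, 1, 1, 1 |

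The matrix has rank 3 for 4 parameters. The contrasts are:

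- iNO − CONT = b1
- iNO-RM − iNO = b2 + b3

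Moving any amount from b2 to b3 leaves all three means unchanged.

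**Step 2: a numerical illustration.** Take 15 points as the scale, with b0 = 0 and b1 = 15.

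| Truth | b2 | b3 | CONT | iNO | iNO-RM |
|---|---|---|---|---|---|
| Antagonism | 30 | −15 | 0 | 15 | 0 + 15 + 30 − 15 = 30 |
| Additivity | 15 | 0 | 0 | 15 | 0 + 15 + 15 + 0 = 30 |
| Pure interaction | 0 | 15 | 0 | 15 | 0 + 15 + 0 + 15 = 30 |

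The data would be the same in all three cases, whatever the number of patients.

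**Step 3: do the repeated measurements help?** No. In the iNO groups iNO is already running at T2. Even if recruitment follows T2, the change from T2 to T3 in iNO-RM compared with iNO is recruitment given on top of iNO, which is again b2 + b3. The repeated-measures ANOVA with one three-level factor cannot separate them, and with these arms no other model could.

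**Step 4: how often an additive effect would look like support.** Assume b2 = 15, b3 = 0, 18 versus 18, and a two-sided t-test at 0.05 with 34 degrees of freedom (critical value 2.032). The noncentrality is 15 / (SD × √(2/18)).

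| Assumed SD | Noncentrality | Chance that iNO-RM vs iNO is significant |
|---|---|---|
| 10 | 4.50 | 99% |
| 15.6 | 2.88 | 80% |
| 20 | 2.25 | 59% |
| 25 | 1.80 | 42% |

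These are ordinary powers for one contrast at assumed SDs. They show how readily a significant difference arises when the interaction is exactly zero.

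**Step 5: what testing synergy would take.** A recruitment-only arm brings the design to rank 4 of 4. The interaction contrast then has standard error SD × √(4/n per arm). At SD 16.1, 80% power for a 15-point interaction needs n = 4 × (16.06 × 2.802 / 15)² = 4 × 3² = 36 per arm, or 4 × 36 = 144 patients. Four arms of 18 (72 patients) would give about 51% power.

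**The case against.** The strongest reply is that this is an overclaim in wording and invalidates no planned analysis. Synergy appears in one clause of the hypothesis and, as a possibility, in the rationale. No aim names it, no effect size is planned for it, no test is assigned to it, and no rule says that a benefit of iNO-RM over iNO will be declared synergy. The trial is described as physiological, and the effect of iNO and the effect of adding recruitment to iNO can both be estimated. All of that is true, and it is why rewording is enough. It does not remove the fault: the clause is part of the only formal hypothesis, and the result that the protocol's own premise predicts would seem to confirm it.

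Smaller points also have some force. The powers in Step 4 rest on assumed SDs, treat a relative improvement as points, and take one variable where the protocol names several. They are illustration only. The primary aim names no comparator; the comparison with standard care sits in the secondary aim. Figure 1 is not shown, so the timing is read from the text, which describes no period of recruitment without iNO.

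Leaving the matter to a statistical analysis plan would not help, because no analysis can estimate a parameter that the arms do not identify. Importing a recruitment effect from elsewhere would be a non-randomised comparison. None is planned, and section 5.8.1 itself says that studies of the response to these interventions are too few.

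**Conclusion.** The hypothesis is wrong as written for this design. The synergy clause cannot be confirmed at 54 patients or at any other number, because the three arms give only the sum of the recruitment effect and the interaction. This needs no assumption about SD, power or effect size. It assumes only that, as the text describes, recruitment is never given without iNO.

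The design is not wholly silent on synergy. If recruitment alone does help, as the protocol holds, then finding iNO-RM no better than iNO would count against synergy. It cannot count for it. The iNO versus CONT contrast, and with it the first part of the hypothesis, is unaffected.

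**What to change.** Keep the three arms and change the wording in three places.

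1. **Section 2.** Replace the synergy clause with a statement about the added effect of recruitment plus individualised PEEP in patients already receiving iNO, tested as iNO-RM versus iNO.
2. **Section 3, first secondary aim.** Name two contrasts: iNO versus CONT, and iNO-RM versus iNO. This also removes the ambiguity about a recruitment-only comparison.
3. **Section 5.8.** State that iNO-RM minus iNO estimates the recruitment effect plus any interaction, and that a benefit of iNO-RM over iNO will not be interpreted as synergy.

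The mention of possible synergy in the Introduction can stay as rationale if it is marked as not tested.

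The cost is a narrower claim, with no change to arms, sample size or procedures. If the sponsor wants the synergy question answered, the alternative is a recruitment-only arm sized for the interaction. Under the assumptions in Step 5 that means about 144 patients in place of 54, which is a different trial.

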5.8.1 Sample Size

At the participating hospital (Hospital Universitario de la Princesa), cardiac surgery provides a continuous daily flow of patients (one or two per day) who could potentially become candidates for the study if they meet inclusion criteria and not exclusion criteria. Assuming a 15% improvement in right ventricular function measured by echocardiographic parameters in response to iNO or pulmonary recruitment (9) and a confidence level of 95%, the estimated sample size will be 54 patients, 18 in each group (27 per center). However, due to the lack of

Versión 2: September 1, 2023

sufficient studies analyzing right ventricular response to iNO, RM, or both, the final sample size may be adjusted based on preliminary results from initial pilot patients and study progress.

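### The primary aim names no comparator and iNO versus standard care is ranked as secondary, while the 15% planning effect is not defined as either a change from baseline or a difference from control

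*Protocol*

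**What the plan says.** Section 3 (Aims) states the primary aim as "To study the effects of inhaled iNO on pulmonary vascular mechanics, right ventricular function, and right ventricular-vascular coupling" in patients early after cardiac surgery. No comparator is named. The secondary aim begins "To compare the effects of iNO with standard care and with a lung recruitment maneuver" and covers the same three outcome domains.

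Section 5.1 describes a controlled, randomised study. Section 5.7 randomises patients to CONT, iNO, or iNO plus recruitment (iNO-RM).

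Section 5.8.1 sizes the trial at 54 patients, 18 per group, with 95% confidence, on this basis: "Assuming a 15% improvement in right ventricular function measured by echocardiographic parameters in response to iNO or pulmonary recruitment". It gives no SD, power or sidedness, and does not say what the improvement is measured against.

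Section 5.8.2 lists t-tests and Wilcoxon tests (paired or unpaired is not stated), ANOVA or Kruskal-Wallis for more than two groups, and repeated measures ANOVA with intervention type as main factor for evolution over time. If data are non-normal, the last is replaced by the Friedman test. No test is linked to the primary aim.

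**The concern.** Measurements fall within the first 2 to 3 hours after surgery. The Introduction attributes right ventricular dysfunction in this setting to bypass-related inflammation, reduced NO production, ischaemia-reperfusion and lung collapse, so the untreated course need not be flat. A change from T1 to T3 within the iNO arm mixes any drug effect with that course. Only the contrast with CONT is protected by randomisation, and section 3 ranks that contrast as secondary.

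Two things are at stake. One is whether the headline result can be attributed to iNO. The other is whether 18 per group is enough, because a 15% change within an arm and a 15% difference between arms need different numbers of patients.

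**Working it through.** **1. Can the primary aim be traced to a test?**
- Section 3: primary aim without comparator; comparison with standard care secondary.
- Sections 5.1 and 5.7: randomised, with CONT.
- Section 5.8.2: between-group tools exist, none assigned to the primary aim. The Friedman test ranks time points within patients and has no term for arm. If normality fails, the analysis named for change over time no longer compares arms.

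**2. Can 18 per group be reproduced?** Not directly, because SD, power and sidedness are absent. Solving backwards with δ = 15%, two-sided α = 0.05 and 80% power (z sum 1.960 + 0.842 = 2.802):
- Between arms, n = 2·(SD·2.802/δ)². For n = 18, SD = 15/(2.802 × √(2/18)) = 16.1%.
- Within arm, n = (SD·2.802/δ)². For n = 18, SD of change = 15 × √18/2.802 = 22.7%.

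At 90% power the values are 13.9% and 19.6%. Either reading fits some SD, so the figure does not reveal which was meant.

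**3. Before-after test when iNO has no effect.** Paired t-test, n = 18, 17 degrees of freedom, two-sided 0.05, noncentrality = drift/SD × √18. Drift and SD are assumptions; the protocol gives neither.

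| Assumed drift | SD of change | Noncentrality | Significant improvement |
|---|---|---|---|
| 0% | any | 0 | 2.5% |
| 5% | 20% | 1.06 | 17% |
| 5% | 15% | 1.41 | 27% |
| 7.5% | 20% | 1.59 | 32% |
| 7.5% | 15% | 2.12 | 52% |
| 10% | 20% | 2.12 | 52% |
| 10% | 15% | 2.83 | 76% |

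A test of iNO against CONT on the same data keeps its 5% two-sided level, because drift common to both arms cancels.

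**4. Power for 15% with 18 per arm, same SD of change under both readings.**
- SD 20%: within arm, noncentrality 15/20 × √18 = 3.18, power 85%. Between arms, 15/(20 × √(2/18)) = 2.25, power 59%; 80% power would need 2·(20 × 2.802/15)² = 27.9, so 28 per arm.
- SD 15%: within arm 98%; between arms 83%.

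**5. If the 15% is a within-arm response and CONT improves by an assumed 5%**, the contrast is 15 − 5 = 10%.
- SD 16%: power 44%; n = 2·(16 × 2.802/10)² = 40.2, so 41 per arm.
- SD 20%: power 31%; n = 2·(20 × 2.802/10)² = 62.8, so 63 per arm.

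**6. What 18 per arm can detect between arms** (80% power, normal approximation): δ = 2.802 × √(2/18) × SD = 0.934 × SD, which is 14.0% at SD 15% and 18.7% at SD 20%.

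**The case against.** In a controlled, randomised study, the effect of a treatment is ordinarily understood as its effect against control. Section 5.8.2 has the tools for this, and Kruskal-Wallis gives a rank-based comparison between groups that could be applied to changes. A statistical analysis plan, not at hand, may name the contrast. All of this stands, and it limits the point: the control arm is there, and the defect lies in how the aims are ranked and in tests not being tied to them. It does not remove the point, because the ranking is stated in the protocol rather than left open.

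A reader might go further and infer that the protocol commits to a before-after analysis, leaving CONT without a role in the main question. The documents do not support that: no section prescribes a single-arm paired test as the primary analysis, and intervention type is the main factor in the repeated measures ANOVA.

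A reader might also infer that the 15% is a before-after figure. The wording leans that way but does not settle it; the cited source is not at hand, and step 2 shows that 18 per group fits either reading. The figure is also stated for iNO or recruitment, not for iNO alone.

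Finally, the drift is hypothetical. Section 4 selects stable patients, T1 is taken once they are stable, and section 6.1 puts iNO administration at about one hour. Drift could be near zero, or negative if persisting collapse raises pulmonary vascular resistance, as the Introduction describes. That is why the percentages in step 3 are illustrations and not estimates.

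**Conclusion.** The point holds as a defect of specification that should be corrected. The stated hierarchy puts the only randomised comparison of iNO with standard care below an aim that has no comparator, and the rest of the protocol leaves room for a within-arm change to be reported as the primary result. The 15% in section 5.8.1 is undefined; it is not shown to be wrong.

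The possible size depends on assumed values: a 17% to 76% chance of a significant improvement without any iNO effect (drift 5% to 10%, SD of change 15% to 20%), and 85% against 59% power for a 15% effect at SD 20%. With no drift, a before-after test would not be biased in this way, but the plan would still be sized on an unidentified quantity.

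**What to change.** - Section 3: make the primary aim the difference between iNO and CONT in change from T1 to T3 in the primary right ventricular variable or variables, and say which of the five listed in section 5.2.2 are meant. Name T1 explicitly, because section 5.7.2 labels T2 as baseline although iNO is already running by then in the treated arms.
- Section 5.8.2: tie a between-arm test of that change to the primary aim, including a between-arm method for non-normal data in place of Friedman. Report within-arm changes descriptively.
- Section 5.8.1: check the source of the 15% and state whether it is a change from baseline or a difference from CONT. It should not simply be declared a between-arm difference. If it is a within-arm figure, restate what 18 per group can detect between arms, with the SD, power and sidedness used.

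The edits are wording only and add no procedures. The real cost is that the sample-size justification may look less favourable, particularly if controls also improve.
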